Figure 4. Protocol of the experimental visits. Visits will be identical except for the oral drug or supplement administration before any procedure.

STATISTICAL ANALYSES: Sample size estimation (statulator.com) is 11 individuals per group, based on the femoral artery blood flow response to knee extension exercise from our preliminary data (see below), using Student's *t*-test for independent samples, and considering a two-tailed alpha of 0.05, and power of 0.8 as parameters. This estimated sample size is adequate relative to our previous investigations^{10,11}. Due to potential influence of sex and race on vascular function⁶⁹, we will duplicate the estimated sample size to recruit an equal number of men and women. To account for incompleteness and exclusion of data during analyses, additional participants will be recruited, leading to an estimate of 30 individuals enrolled in each racial group. We will use a mixed-model ANOVA to compare vascular responses according to the effects of drug administration (Placebo vs. Drug), group (Black vs. White), and interaction. Subjects' characteristics will be compared using Student's *t*-test for independent samples and, in case of significant differences, such characteristics will be used as covariates in the ANOVA. Additionally, while men and women will be primarily grouped according to race, the large and balanced sample size will allow for sub-analyses comparing the effects of race on vascular responses separately in men and women.

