Purpose	
To begin to elucidate the alterations in vascular function in Black individuals, we chose to target ET-1, a peptide produced by the vascular endothelium that mediates vasoconstriction by binding ET_A and ET_B receptors on smooth muscle^{14,15}. ET-1 seems to play a prominent role in the pathophysiology of hypertension specifically in Black patients^{16,17}. Also, it is suggested that ET-1 may be associated with impaired vascular control of blood pressure in young normotensive Black men¹⁸. Vascular responsiveness to ET-1 is also upregulated in adults exposed to insults during their fetal life (e.g., poor maternal nutrition, chronic stress, no prenatal care), psychological stressors during childhood (e.g., physical and emotional abuse, household dysfunction), and high ethnic discrimination¹⁹⁻²⁴—all of which are more prevalent among Black than White individuals, possibly contributing to racial disparities in vascular function²⁵⁻²⁸. We hypothesize that Black individuals have reduced vasodilator responses as a consequence of a greater vasoconstrictor tone mediated by ET-1. Therefore, we hypothesize that the antagonism of ET_A and ET_B receptors will reduce the vasoconstrictor tone and augment the vasodilator responses in Black but not in White individuals.

Specific Aim	
We will examine the role of ET-1 on brachial and popliteal artery flow-mediated dilation, reactive hyperemia, and blood flow responses to passive leg movement, rhythmic handgrip exercise, and rhythmic knee extension exercise between Black and White individuals. Using an acute oral administration of Bosentan, we will antagonize ET_A and ET_B receptors to reduce the vasoconstrictor tone mediated by ET-1 and, consequently, allow for greater flow-mediated dilation, reactive hyperemia, and blood flow responses to passive leg movement, handgrip, and knee extension. We anticipate that this effect of Bosentan will be more prominent in Black individuals than in White individuals. In a separate visit, the participants will receive a Placebo to serve as a control. We will also examine prenatal and at-birth medical records, and apply questionnaires of adverse childhood experiences and perceived discrimination to assess whether these early-life risk factors are associated with racial disparities in vasodilation between Black and White individuals.

Study Period	
3 years Anticipated start date: 09/01/2020 Anticipated end date: 09/01/2023

Data Generation Period	N/A

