
Study Design
	
The study will consist of three visits to the research clinic (Clinical Research and Trials Unit at the UMMC campus) over 4 months. If a participant misses an appointment, rescheduling will be attempted twice. Women will provide a urine sample for a pregnancy test and answer questions about the most recent menstrual period before any research measurement or procedure be performed in any visit.
 
Visit 1: Informed Consent Form, written consent for access to their prenatal and at-birth medical records, assessment of medical history, application of the questionnaires “Adverse Childhood Experiences (ACE)” and “Scale of Ethnic Experiences (SEE)”, collection of blood samples and endothelial cells from the antecubital vein, familiarization with measurements and procedures that will take place in the next visits, and a rhythmic knee extension maximal exercise test. Visit 1 will last for about 2 hours.
 
Visit 2: Qualifying participants will participate in Visit 2 within 4 weeks after Visit 1. At the beginning of the visit, we will randomly administer either a single oral dose of Bosentan (125 mg) or Placebo. Two hours after administration, we will perform the research measurements and procedures as explained below. This visit will last for about 4 hours.
 
Visit 3: Those who complete Visit 2 will participate in Visit 3, which will take place 1 to 12 weeks later. All research measurements and procedures will be identical, except for the drug administration. At the beginning of the visit, we will administer either Bosentan (125 mg) or Placebo, whichever was not administered in Visit 2.
 
Summary of the Research Measurements:
 
 • Anthropometrics: Height, weight, waist, and hip for characterization. • Electrocardiogram: Adhesive patches placed on the chest and abdomen for heart rate. • Respiration: An elastic belt placed around the abdomen for respiratory movements. • Blood pressure: Brachial blood pressure will be measured throughout the study with an automated blood pressure monitor for validation of the finger blood pressure values. • Finger blood pressure: A small cuff placed around one of the fingers for continuous recording of beat-to-beat blood pressure. • Arm blood flow: Duplex Doppler ultrasound will be used for measurements of brachial artery diameter and blood velocity, used for calculation of blood flow. • Leg blood flow: Duplex Doppler ultrasound will be used for measurements of popliteal and femoral artery diameter and blood velocity, used for calculation of blood flow.

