Inclusion Criteria	
 • Black (i.e. African American) or White (i.e. Caucasian American) individuals • 18 to 35 years of age • Born and raised in the United States • Biological parents of the same race (i.e. either Black or White)

Exclusion Criteria	
 • Known chronic or ongoing disease, or on prescribed pharmacological treatment • History of liver disease • Pregnant, trying to become pregnant, or breastfeeding women • Use of hormonal contraceptives • Smoking or vaping in the last 6 months • Body mass index > 35 kg/m²
Number of Participants (anticipated)	
50 participants (i.e. 25 on each racial group). Based on data from Schreuder et al.³⁰, taking the improvement of blood flow response to rhythmic handgrip with Bosentan as the primary outcome, the estimated sample size is 42 participants (i.e. 21 per group). We anticipate having to recruit about 20% more individuals to account for possible loss of data (e.g. participants who cannot complete all visits, problems during analyses, etc.), therefore needing to enroll 50 participants.

Screening and Consent Process	
Announcements will be made via UMMC e-mail listserv, UMMC intranet, Research Participant Recruitment app, flyers on campus, and word of mouth. Potential participants will contact the study personnel via e-mail or phone, and answer screening questions. If they meet the inclusion criteria, Visit 1 will be scheduled. Consenting will be conducted in Visit 1 at the research clinic by [name] or by a study person after supervision and adequate training with [name]. Following consenting, there will be assessments of medical history, and familiarization with the research measurements and procedures. After that, those who qualify for the study will be scheduled for Visit 2 and, subsequently, Visit 3.

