----------------------------------	---

	
office in a locked cabinet. Only the Principal Investigator and study personnel will have access to the files via key. No other students or faculty will have access.
 
 ACE and SEE questionnaires: Given the sensitive nature of the topics assessed with these psychometric tests, participants will be informed that they may experience some distress or discomfort, may decline to answer any question, and may request to interrupt or end the assessment at any time. Our research personnel will observe the participants and may also interrupt or end the assessment if it seems necessary. In the event of an emergent psychiatric crisis, [name] and the research personnel will take appropriate steps including calling an emergency contact person indicated by the participant in the Medical History Form, and facilitating transportation to emergency health care. Furthermore, all participants will receive referral information and telephone numbers for local and national emotional support services, such as the Student Counseling and Wellness Center, the Center for Integrative Health, the Behavioral Health Specialty Clinic, Crisis and Suicide Prevention lines. 
Benefits:
 
 There will be no direct benefit from participating in this research study. We hope to learn information that may help others in the future.
Randomization and blinding	
We will use a Randomization Model tool in the REDCap system to randomly select between Bosentan and Placebo to be administered on Visit 2 for each individual, aiming at achieving a balanced distribution between Black and White individuals, and between men and women. Once the random drug selection is made for Visit 2, selection for Visit 3 will automatically be the alternative drug. Therefore, participants who complete Visits 2 and 3 will have received both Bosentan and Placebo. The participants and study personnel will be blind to the administration of Bosentan or Placebo on any visit. Pharmacists of the Investigational Drug Services at UMMC will retain the information about the drug selection per visit and will reveal it to the study personnel after completing data collection and analyses for that study participant or in case of emergency health care.

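### Releasing bosentan/placebo codes to the study team one participant at a time weakens assessor blinding for later participants and permits unblinded looks at the drug-by-race comparison

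*Combined protocol and SAP*

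**What the plan says.** The rule is in the Research Protocol for the bosentan study, under Randomization and blinding. The double-blind commitment there is explicit: "The participants and study personnel will be blind to the administration of Bosentan or Placebo on any visit". The pharmacists keep the allocation and "will reveal it to the study personnel after completing data collection and analyses for that study participant", or earlier if emergency care is needed. One code covers both treatment visits: "Once the random drug selection is made for Visit 2, selection for Visit 3 will automatically be the alternative drug". Allocation is made with a REDCap randomization tool, "aiming at achieving a balanced distribution between Black and White individuals, and between men and women"; the method, strata and any block size are not stated.

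The Study Period entry reads "3 years Anticipated start date: 09/01/2020 Anticipated end date: 09/01/2023". Under Study Design, each participant makes three visits over four months, with Visit 3 following Visit 2 by an interval given as "which will take place 1 to 12 weeks later". The Data Safety Monitoring Plan entry provides semi-annual meetings with one monitor. No interim efficacy analysis, stopping boundary or alpha adjustment is described.

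The grant section (Approach, Study Design) calls Aims 1 and 2 double-blind but gives no code-release rule.

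**The concern.** The people who must stay blind are the people who receive the codes, and they receive them person by person. No separate unblinded staff, sealed period or rule against pooling released results is described.

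Three features of this trial make that matter.

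- The hypothesis is directional by race (Purpose; Study Endpoint): bosentan should help Black but not White participants. No masking of race is described, so drug blinding is the only described protection for the drug-by-race contrast.
- The main outcomes are ultrasound diameters, velocities and flows (Outcome Measures), whose acquisition and reading involve operator judgement.
- Data exclusions are expected without stated criteria. The grant section's Statistical Analyses over-recruits "To account for incompleteness and exclusion of data during analyses", and the bosentan protocol's sample-size entry likewise allows for problems during analyses.

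Knowledge of how earlier participants responded, and possibly a better-than-chance guess at a later sequence, could colour reading or exclusion in later participants. The team could also test the comparison repeatedly with no control of error. A code cannot be resealed once released, so neither problem can be repaired at analysis.

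**Working it through.** **1. How long the exposure could last.** Study period 3 years = 36 months; one participant's visits span 4 months. If the first participants' analyses follow promptly, release could begin with up to 36 − 4 = 32 months of the study period remaining. The actual figure depends on enrolment pace and on how quickly each participant is analysed, neither of which is stated.

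**2. The plan's own figure.** The bosentan protocol estimates 42 participants and adds about 20%: 42 × 1.20 = 50.4, which reproduces its enrolment of 50 (25 per racial group). That figure is not in dispute; it sets the horizon for steps 3 and 4. The 42 itself cannot be re-derived, because no effect size, SD, alpha or power accompanies it.

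**3. Predictability of later sequences.** *Assumption, not in the documents:* permuted blocks within the four race-by-sex cells, with every earlier code in the cell known. In a block of size 2m, an assignment is certain once one sequence has been used up. The expected number of such assignments is 2m/(m+1), so the share is 1/(m+1).

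- Block 2 (m = 1): 1/2 = 50%.
- Block 4 (m = 2): 1/3 = 33%. Directly: the fourth place is always certain and the third is certain with probability 1/3, giving (1 + 1/3)/4 = 1/3.
- Block 6 (m = 3): 1/4 = 25%.

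Simulation with 12 participants per cell (50/4 = 12.5) gave 0.500, 0.334 and 0.251. The accuracy of the best guess was 75%, 71% and 68%, against 50% with codes sealed. For block 2 this is (0.5 + 1)/2 = 0.75; for block 4, (1/2 + 2/3 + 2/3 + 1)/4 = 0.708. Under simple randomization, guessing stays at 50% whatever has been revealed.

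These are upper bounds. Participants overlap, so some earlier codes in a cell would still be sealed when a later person is measured.

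**4. Type I error if the team looked and acted.** *Assumptions:* the drug-by-group interaction is tested by a two-sample t-test on within-person drug-minus-placebo differences, with 25 per group, nominal two-sided 0.05, no true effect and 40,000 simulated trials. The 0.05 level comes from the grant section; the bosentan protocol states none. A significant result at any look counts as a rejection.

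| Looks (number per group at each) | Type I error |
|---|---|
| 1 (25) | 0.050 |
| 2 (13, 25) | 0.081 |
| 5 (5, 10, 15, 20, 25) | 0.145 |
| 6 (4, 8, 12, 17, 21, 25), about semi-annual | 0.161 |
| After every pair from 5 to 25 | 0.204 |

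The first row is also the result with codes held to lock: a single unblinded test, with the nominal level kept. It equally applies under the present rule if nobody tests early or acts on what they see.

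**5. What cannot be calculated.** The documents give no basis for quantifying expectation bias in image reading or exclusion.

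**The case against.** A reader might infer that double-blinding is lost for everyone after the first release. The text does not support that. Participants and personnel are to be blind at every visit, and a code is released only after that person's data collection and analyses. Later participants are therefore measured and analysed with their own codes sealed, and exclusions made within a participant's analysis are made before that participant's code is known.

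A reader might also take 42, 50 and 60 as possible stopping sizes. They are not. The first two are the requirement and the enrolment of one plan; 60 belongs to the four-intervention grant proposal. No interim efficacy test is planned, so error inflation is a possibility and not a feature of the design.

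Three further points have force. Blocks are nowhere stated, and the balance aim could be met in other ways. Every completer receives both drugs, so foreseeing a sequence cannot steer a person towards one treatment; what remains is assessor expectation. And the documents say only *study personnel*: they do not state that the same individuals acquire images, read them and decide exclusions.

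Finally, under Risks and benefits, stored samples are to be assayed together. If *analyses* in the release rule includes those assays, release would come much later. The text does not say so; if that was the intent, the fix below simply states it.

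These points limit the size of the problem but leave the rule standing: release is per participant, with no safeguard for those still to be measured.

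**Conclusion.** The point holds in a limited form and should be fixed. In the bosentan protocol, per-participant release weakens assessor blinding for later participants and leaves the drug-by-race comparison open to uncontrolled unblinded looks.

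The predictability figures in step 3 are ceilings that rest on assumed blocks and complete knowledge of earlier codes; simple randomization would add no predictability. The error rates in step 4 apply only if someone tests without adjustment and acts on the result. The documents do not show that either has happened or is intended.

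For Aims 1a–1c there is no release rule to fault, so extending the change to them is a precaution and not the correction of a shown error.

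**What to change.** Replace the release rule under Randomization and blinding with:

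> Codes are released to study personnel only after the last participant has completed Visit 3, all images have been analysed, all exclusions have been decided and the database is locked, or in case of emergency health care.

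This keeps the existing emergency exception. As a precaution, state the same rule for Aims 1a–1c, with the last study visit of each aim in place of Visit 3.

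The cost is one sentence in the protocol and an instruction to the pharmacy. Sample size, visits and procedures are unchanged, and nothing in the documents requires earlier release outside emergencies.

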Outcome Measures	The primary measurements obtained by duplex Doppler ultrasound are: 1) brachial artery flow-mediated dilation (i.e., the increase in arterial diameter in response to the increased shear stress following forearm cuff release); 2) forearm reactive hyperemia (i.e., the increase in blood velocity following forearm cuff release); 3) blood flow responses to passive leg movement; 4) blood flow responses to low, moderate, and high-intensity rhythmic handgrip exercise; 5) blood flow responses to low, moderate, and high-intensity rhythmic knee extension exercise. Other measurements are beat-to-beat heart rate and beat-to-beat blood pressure, which can be used for further analyses of heart rate variability, blood pressure variability, and baroreflex sensitivity.
Study Endpoint	To determine whether there is an augmented contribution of ET-1 to the basal vascular tone in Black individuals compared with White individuals. We anticipate that the antagonism of ET-1 receptors will improve vasodilator responses in Black individuals but not in White individuals.
Data Safety Monitoring Plan	[name] Jr., Professor of the Department of Medicine, will serve as an independent Data Safety Monitor for this study. The study personnel will conduct semi-annual meetings with the Monitor to present the research progress and discussion of observed events upon drug administration. In case of a participant's emergency health care that could be associated with the study, the study personnel will notify the Monitor within 24 h.
Protected Health Information (PHI)	The information collected in this study includes name, telephone, home address, e-mail address, date of birth, age, race and ethnicity, medical history, and pictures. Each study participant will be given a study ID and the data will be associated with this ID. All data will be accessed via HIPAA compliant methods and stored using REDCap.
Statistical Methodology	Flow-mediated dilation and reactive hyperemia will be compared between groups (Black vs. White) and between drugs (Bosentan vs. Placebo) using a mixed model ANOVA (two-way). Responses to rhythmic handgrip exercise will be compared between groups (Black vs. White), between drugs (Bosentan vs. Placebo), and between intensities (low, moderate, high) using a mixed model ANOVA (three-way).

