Sample size estimation (statulator.com) is 11 individuals per group, based on the femoral artery blood flow response to knee extension exercise from our preliminary data, using Student's t-test for independent samples, and considering a two-tailed alpha of 0.05, and power of 0.8 as parameters. This estimated sample size is adequate relative to our previous investigations. Due to potential influence of sex and race on vascular function, we will duplicate the estimated sample size to recruit an equal number of men and women. To account for incompleteness and exclusion of data during analyses, additional participants will be recruited, leading to an estimate of 30 individuals enrolled in each racial group. We will use a mixed-model ANOVA to compare vascular responses according to the effects of drug administration (Placebo vs. Drug), group (Black vs. White), and interaction. Subjects' characteristics will be compared using Student's t-test for independent samples and, in case of significant differences, such characteristics will be used as covariates in the ANOVA. Additionally, while men and women will be primarily grouped according to race, the large and balanced sample size will allow for sub-analyses comparing the effects of race on vascular responses separately in men and women.

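### The bosentan protocol names one primary outcome where it sets the sample size but lists five unranked primary measurements where it defines outcomes, and it names neither a decisive test nor a multiplicity rule

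*Combined protocol and SAP*

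**What the plan says.** Three places bear on what is primary.

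- **Research Protocol (bosentan), Number of Participants:** "taking the improvement of blood flow response to rhythmic handgrip with Bosentan as the primary outcome, the estimated sample size is 42 participants", that is, 21 per group. No alpha, power, effect size or standard deviation is given. Enrolment is then raised to 50: "We anticipate having to recruit about 20% more individuals to account for possible loss of data".
- **Research Protocol, Outcome Measures:** "The primary measurements obtained by duplex Doppler ultrasound are: 1) brachial artery flow-mediated dilation", followed by forearm reactive hyperemia, passive leg movement, handgrip at three intensities and knee extension at three intensities. Heart rate and blood pressure are set apart as other measurements. The five are not ranked.
- **Research Strategy, Statistical Analyses, repeated in Statistical Design and Power:** the calculation arrives at 11 per group. Its endpoint is given as "based on the femoral artery blood flow response to knee extension exercise from our preliminary data" and its error rates as "considering a two-tailed alpha of 0.05, and power of 0.8 as parameters". This covers the four-intervention project, whose Aim 2 is bosentan. Knee extension is not called a primary outcome there.

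On analysis, the Research Protocol's Statistical Methodology gives flow-mediated dilation and reactive hyperemia a two-way mixed-model ANOVA. For handgrip it says "Responses to rhythmic handgrip exercise will be compared between groups (Black vs. White), between drugs (Bosentan vs. Placebo), and between intensities (low, moderate, high"); that model is three-way. It assigns no model to passive leg movement or knee extension and does not mention an interaction. The project-level sections plan a mixed-model ANOVA of vascular responses with drug, group and interaction effects, without saying which one decides. None of these sections has a multiplicity rule. The Study Endpoint expects better vasodilator responses in one racial group and not the other, without tying this to a measurement.

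**The concern.** A study cannot have both a single primary outcome and five unranked ones. The reader cannot tell which result the trial stands or falls on. The expected finding is worded for vasodilator responses in general, so a favourable result on any of the five could be presented as the planned confirmation.

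The decisive term is also open. A benefit in one group and not the other is a difference between drug effects, so it needs the group-by-drug interaction. A two-way model has three effects (two main effects and one interaction). The three-way handgrip model has seven (three main effects, three two-way interactions and one three-way interaction), and two of those contain group by drug. The protocol does not say which effect answers the question. At stake is whether a reported positive result carries a 5% error rate or that of the best of several tests.

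**Working it through.** **The plan's own figures.** The step from 42 to 50 reproduces: 42 × 1.2 = 50.4. The 42 itself cannot be reproduced, because its inputs are not stated. The 11 per group cannot be reproduced forward either, because the text gives no mean difference or standard deviation. Solved backwards with an independent t-test (two-sided 0.05, power 0.80), it implies a standardized difference of about 1.26. The only alpha in the documents is the 0.05 of this knee-extension calculation, and it applies to one test. No family-wise error rate is stated.

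**Inputs for the error rate.**
- Number of outcomes, k = 5 (Outcome Measures).
- Two-sided 0.05 per test. This is stated only for the knee-extension sizing and is assumed here for the ANOVA tests.
- One group-by-drug test per outcome (assumption, following the hypothesis).
- Any one significant result counts as support (assumption; the documents set no success rule).
- A common correlation r between outcomes. The documents give none, so r is varied from 0 to 0.9.

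**Independent outcomes.** Chance of at least one false positive = 1 − (1 − 0.05)^k.
- k = 1: 5.0%
- k = 5: 1 − 0.95^5 = 1 − 0.774 = 22.6%

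**Correlated outcomes, k = 5.** Simulation of equally correlated normal statistics, 400,000 draws per value:

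| r | 0 | 0.2 | 0.3 | 0.5 | 0.7 | 0.8 | 0.9 |
|---|---|---|---|---|---|---|---|
| At least one false positive | 22.6% | 21.8% | 20.8% | 18.3% | 14.9% | 12.7% | 10.2% |

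With period effects left out, the group-by-drug test is a two-sample comparison of each person's bosentan-minus-placebo difference. Simulating that comparison with t-tests, 21 per group and 40,000 trials gives 22.3%, 21.0%, 18.2% and 12.9% at r = 0, 0.3, 0.5 and 0.8, in agreement with the table.

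**Predicted direction only.** If only an interaction favouring Black participants counted, the per-test rate would be 2.5%. Five independent tests give 1 − 0.975^5 = 11.9%, and r = 0.5 gives about 9%. These are roughly half the two-sided figures, set against a comparator that is also halved.

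**After the fix.** One outcome and one test: 5.0%. If all five were kept as co-primary with Bonferroni at 0.05/5 = 0.01 each: 1 − 0.99^5 = 4.9% if independent, and never above 5%.

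**The case against.** The best defence is that a primary outcome is already named. Only Number of Participants uses that term, and it names handgrip. The list under Outcome Measures can be read as separating ultrasound measurements from heart rate and blood pressure, not as declaring five co-primary hypotheses. The study is also mechanistic and meant partly to produce preliminary data. That reading is possible, but the text does not settle it, and neither section refers to the other. The missing decisive term and multiplicity rule remain on either reading.

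Three stronger readings are tempting, and the documents do not support them.

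- *Three rival primary outcomes.* Knee extension is the sizing basis for the wider project and one of the five measurements. It is nowhere called the primary outcome.
- *A false-positive rate of 20% to 30% as a fact about the trial.* No section says that one significant result in five is success. The outcomes come from the same people at the same visits, so positive correlation is plausible, and at r = 0.5 the rate is already 18%. A figure of 30% needs seven independent tests (1 − 0.95^7 = 30.2%). Those would include two group-by-drug-by-intensity terms, which are not the stated hypothesis, one of them from a knee-extension model that the protocol does not specify.
- *No analysis at all for passive leg movement and knee extension.* The gap is in the bosentan protocol's Statistical Methodology. The project-level sections give a generic drug, group and interaction ANOVA that would cover both, though without an intensity factor.

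**Conclusion.** The concern holds as an unresolved conflict over what is primary, together with an unnamed decisive test and no multiplicity rule. Its size is conditional. If any one of five two-sided group-by-drug tests at 0.05 counted as support, the false-positive rate would be about 10% (r = 0.9) to 23% (r = 0), against 5% for one named test. This rests on one test per outcome, an any-of-five success rule and a common correlation, none of which the documents state. At every correlation tried the rate is at least twice the nominal level. If the handgrip interaction alone is taken as decisive, there is no inflation, but the plan does not say so.

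**What to change.** 1. In the Research Protocol's Outcome Measures, make handgrip blood flow, the outcome already used for its sample size, the sole primary outcome.
2. In its Statistical Methodology, name one primary test at two-sided 0.05: the group-by-drug term of the planned three-way handgrip model, which is the effect averaged over intensities.
3. Label flow-mediated dilation, reactive hyperemia, passive leg movement and knee extension as secondary, with Holm adjustment across their four group-by-drug tests. State a two-way model for passive leg movement and a three-way model for knee extension.
4. In the project-level Statistical Analyses and in Statistical Design and Power, say that knee extension is the sizing basis for the wider project and not the primary outcome of the bosentan study.
5. Reconcile the handgrip procedure. The Research Strategy's Experimental Procedures describes a single trial at 30% of maximal voluntary contraction, while the Research Protocol's Abstract, Outcome Measures and Statistical Methodology use three intensities. An effect averaged over intensities exists only under the latter.

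The cost is protocol and analysis-plan wording, with no added participants or measurements. The small downside is that four outcomes lose primary status. Under Randomization and blinding, allocation is released to study personnel participant by participant, so the change should be dated and should record how many allocations were already known.
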